## **E 4 Management of Acute Anaphylaxis**

### **Immediate intervention**

1. Assessment of airway, breathing, circulation, and adequacy of mentation
2. Administer epinephrine intramuscularly every 5-15 minutes, in appropriate doses, as necessary, depending on the presenting signs and symptoms of anaphylaxis, to control signs and symptoms and prevent progression to more severe symptoms such as respiratory distress, hypotension, shock and unconsciousness.

### **Possibly appropriate, subsequent measures depending on response to epinephrine**

- (e) Place subject in recumbent position and elevate lower extremities.
- (f) Establish and maintain airway.
- (g) Administer oxygen.
- (h) Establish venous access.
- (i) Normal saline IV for fluid replacement.

### **Specific measures to consider after epinephrine injections, where appropriate**

- (j) Consider epinephrine infusion.
- (k) Consider H1 and H2 antihistamines.
- (l) Consider nebulized  $\beta_2$  agonist [eg, albuterol (salbutamol)] for bronchospasm resistant to epinephrine.
- (m) Consider systemic corticosteroids.
- (n) Consider vasopressor (e.g. dopamine).
- (o) Consider glucagon for subject taking  $\beta$ -blocker.
- (p) Consider atropine for symptomatic bradycardia.
- (q) Consider transportation to an emergency department or an intensive care facility.
- (r) For cardiopulmonary arrest during anaphylaxis, high-dose epinephrine and prolonged resuscitation efforts are encouraged, if necessary.

Tezepelumab - D5180C00018

Adapted from: Kemp SF, Lockey RF, Simons FE; World Allergy Organization ad hoc Committee on Epinephrine in Anaphylaxis. Epinephrine: the drug of choice for anaphylaxis. A statement of the World Allergy Organization. *Allergy*. 2008; 63(8):1061-70.

[figure not shown]

## **Appendix F Guidance for Changes to Background Asthma Medication adapted from GINA 2018**

### **F 1 Guidance to Step Down of Background Medication**

- Consider stepping down when asthma symptoms have been well controlled and lung function has been stable for 3 or more months, starting from Visit 1. If the subject has risk factors for exacerbations or fixed airflow limitation, do not step down without close supervision.
- Approach each step as a therapeutic trial. Engage the subject in the process; document their asthma status (symptom control, lung function and risk factors); provide clear instructions; and ensure the subject has sufficient medication to resume their previous dose if necessary; monitor symptoms; and schedule a follow-up visit.
- Stepping down ICS doses by 25-50% at 3-month intervals is feasible and safe for most subjects.

Tezepelumab - D5180C00018

**Figure 5 Step Down of Background Medication**

 The additional asthma controller medications or their dose can be increased or decreased as per PI's discretion.

[figure not shown]
 If the subject is not on a combination ICS/LABA and is on a separate ICS and another additional asthma controller medication, reduce only the dose of ICS and continue the same dose of additional asthma controller medications.

**F 2 Guidance to Step Up of Background Medication**

- If the subject's symptoms are worsening after step down of asthma background medication as per [Figure 5](#), they can be up titrated as per [Figure 6](#) below, at the Investigator's discretion.

**Figure 6 Step Up of Asthma Background Medication**

\*If a subject experiences an asthma exacerbation, this should be treated appropriately as per investigator discretion.

Tezepelumab - D5180C00018

**Appendix G Abbreviations**

The following abbreviations and special terms are used in this study Clinical Study Protocol.

Abbreviation or special term	Explanation
AAER	Annualized Asthma Exacerbation Rate
CCI	
ADA	Anti-Drug Antibodies
AE	Adverse Event
AERR	Asthma Exacerbation Reduction Rate
AESI	Adverse Event of Special Interest
ALP	Alkaline Phosphatase
ALT	Alanine Aminotransferase
ATS	American Thoracic Society
ASD	Asthma Symptom Diary
AST	Aspartate Aminotransferase
BD	Bronchodilator
β-HCG	Beta-Human Chorionic Gonadotropin
BUN	Blood Urea Nitrogen
CO 2	Carbon Dioxide
CompEx	Composite Endpoint for Exacerbations
CONSORT	Consolidated Standards of Reporting Trials
COPD	Chronic Obstructive Pulmonary Disease
COVID-19	Corona Virus Disease 2019
CRF	Case Report Form (electronic/paper)
CSA	Clinical Study Agreement
CSR	Clinical Study Report
CTCAE	Common Terminology Criteria for Adverse Event
DAE	Discontinuation of Investigational Product due to Adverse Event
DSMB	Data and Safety Monitoring Board
DUS	Disease under Study
EAR	Early Asthmatic Response

## Tezepelumab - D5180C00018

Abbreviation or special term	Explanation
EC	Ethics Committee, synonymous to Institutional Review Board (IRB) and Independent Ethics Committee (IEC)
ER	Emergency Room
EOT	End of Treatment
ePRO	Electronic Subject Reported Outcome device
EU	European Union
EUA	Emergency Use Authorization
FEIA	Fluorescent Enzyme Immunoassay
CCI	
FeNO	Fractional Exhaled Nitric Oxide
FEV 1	Forced Expiratory Volume in 1 second
FSH	Follicle-Stimulating Hormone
FU	Follow-up
CCI	
GCP	Good Clinical Practice
GGT	Gamma-Glutamyl Transpeptidase
GINA	Global Initiative for Asthma
GLI	Global Lung Function Initiative
GMP	Good Manufacturing Practice
HIV	Human Immunodeficiency Virus
HCP	Health Care Provider
IATA	International Air Transport Association
ICH	International Conference on Harmonization
International Co-ordinating investigator	If a study is conducted in several countries the International Co-ordinating Investigator is the Investigator co-ordinating the investigators and/or activities internationally.
ICF	Informed Consent Form
ICS	Inhaled Corticosteroids
IgE	Immunoglobulin E
IgG	Immunoglobulin G
IL	Interleukin
IL-13	Interleukin-13

Tezepelumab - D5180C00018

Abbreviation or special term	Explanation
IP	Investigational Product
IPD	Investigational Product Discontinuation
IRB	Institutional Review Board
IRT	Interactive Response Technology
ISF	Investigator Study File
ITT	Intent-to-Treat
IUO	Investigational Use Only
LABA	Long-Acting $\beta$ 2-Agonist
LAMA	Long-Acting Muscarinic Antagonists
LAR	Late Asthmatic Response
LIMS	Laboratory Information Management System
LRTI	Low Respiratory Tract Infection
LTE	Long Term Extension
LTRA	Leukotriene Receptor Antagonists
LSLV	Last Subject Last Visit
MAb	Monoclonal Antibody
MACE	Major Adverse Cardiac Events
MAR	Missing at Random
MedDRA	Medical Dictionary for Regulatory Activities
MCID	Minimum Clinically Important Difference
nAB	Neutralizing Antibodies
OCS	Oral Corticosteroids
OAE	Other Significant Adverse Event
PD	Pharmacodynamic
PGx	Genetic research
PGI-S	Subject Global Impression of Severity
PI	Principal Investigator
CCI	
PNV	Predicted Normal Value
CCI	
PT	Preferred Term

Tezepelumab - D5180C00018

Abbreviation or special term	Explanation
Q4W	Every 4 Weeks
SABA	Short-Acting $\beta$ 2-Agonist
SAE	Serious Adverse Event
SAP	Statistical Analysis Plan
SC	Subcutaneous
CCI	
SOA	Schedule of Assessment
SOC	System Organ Class
SDV	Source Data Verification
Th2	T Helper 2 Cells
TLC	Total Lung Capacity
TSLP	Thymic Stromal Lymphopoietin
TSLPR	Thymic Stromal Derived Lymphopoietin Receptor
ULN	Upper Limit of Normal
UNS	Unscheduled
WBDC	Web Based Data Capture
WOCBP	Women of Childbearing Potential

## **Appendix H Changes to the protocol related to the COVID-19 Pandemic**

**Please Note:** Changes below should only be implemented during the COVID-19 pandemic and if allowable by local/regional guidelines.

### **H 1 Home Visits to Replace On-Site Visits (where applicable)**

Due to local travel restrictions and/or site restrictions, subjects may not wish to or may not be able to go to the study site for study visits and related procedures. If an on-site visit is not possible, it is recommended to have a home visit with home administration of IP by a qualified HCP, provided this is acceptable within local regulation/guidance. This is to ensure safety of the trial subjects and minimum disruption to IP administration that may occur during the COVID-19 pandemic.

**NOTE: The first 2 IP administrations in DESTINATION must be done on site.**

Where possible study assessments should be conducted according to the SoA.

At minimum, during home visit the qualified HCP is expected to:

- Collect adverse events
- Review concomitant medications
- Collection information on asthma exacerbation and healthcare resources utilization
- Perform a physical examination
- Collect vital signs
- Conduct urine pregnancy test (dipstick), prior to IP administration, if applicable
- If possible, collect blood and urine sample according to the SoA
- Administer IP
- Observe the subject for one hour after IP administration for the signs or symptoms of any acute drug reactions
- Document the visit

#### **Laboratory assessments during home visit**

Tezepelumab - D5180C00018

If safety blood samples are being collected, they may be obtained post IP administration and during the 1-hour observation period to allow additional time for processing of the safety samples at the site according to the laboratory manual.

CCI

## **H 2 Visits at an Alternate Location (where applicable)**

Study visits including administration of IP and study assessments according to the SoA can take place at an alternative location away from infection risk zones, or closer to subjects' homes, provided this is acceptable within local regulation/guidance.

## **H 3 Phone Call Visit to Replace On-Site Visit (where applicable)**

During the COVID-19 pandemic, on-site visits may be replaced by a remote visit (phone call and/or video conference) if allowed by local/regional guidelines. Having a phone call and/or a video conference with the subject will allow conduct of study procedures including reporting of adverse events, concomitant medication, information on asthma control/exacerbation and healthcare resource utilization.

## **H 4 Subject Rollover Process**

### **For NAVIGATOR subjects pending roll over**

If on-site Randomization and IP administration in the DESTINATION study is not possible by the end of the NAVIGATOR Safety Follow-Up (Visit 19), a subject will not roll-over to DESTINATION.

Subjects aimed to roll over to the DESTINATION study will continue participation in the NAVIGATOR study Safety Follow-Up (Visit 18 and Visit 19, 12 weeks) until the on-site DESTINATION randomization and IP administration can be conducted.

- If the subject is able to attend an on-site Visit 18 of the NAVIGATOR study, they can be randomized into the DESTINATION study at this visit. During this visit the informed consent form, eligibility check, unscheduled safety labs, serum pregnancy test (if applicable) and randomization must be completed along with assessments as per Visit 3 in

Tezepelumab - D5180C00018

DESTINATION Table 1. If Visit 4 cannot be conducted on-site this can be conducted as a phone visit without IP administration. Please note the Home visit with IP administration alternative cannot be used until the first 2 IP doses are administered during an on-site visit.

- If the subject is able to attend an on-site Visit 19 of the NAVIGATOR study, they can be randomized into the DESTINATION study at this visit. During this visit the informed consent form, eligibility check, serum pregnancy test (if applicable) and randomization must be completed along with assessments as per Visit 5 in DESTINATION Table 1. Visit 3 and Visit 4 will be skipped. If Visit 6 cannot be conducted on-site this can be conducted as phone visit without IP administration. Please note the Home visit with IP administration alternative cannot be used until the first 2 IP doses are administered during an on-site visit.

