#### 8.4.3 Overdose

A dose in excess of 280 mg SC administered within a 2-week period is considered an overdose.

There is currently no specific treatment in the event of overdose of IP and possible symptoms of an overdose are not established.

An overdose with associated AEs is recorded as the AE diagnosis/symptoms on the relevant AE modules in the CRF and on the Overdose CRF module.

An overdose without associated symptoms is only reported on the Overdose CRF module.

If an overdose on an AstraZeneca study drug occurs in the course of the study, then the Investigator or other site personnel inform appropriate AstraZeneca representatives immediately, or **no later than 24 hours** of when he or she becomes aware of it.

The designated AstraZeneca representative works with the Investigator to ensure that all relevant information is provided to the AstraZeneca Subject Safety data entry site.

Tezepelumab - D5180C00018

For overdoses associated with a SAE, the standard reporting timelines apply, see Section 8.3.2.

For other overdoses, reporting must occur within 30 days.

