### **For SOURCE subjects pending roll over**

If on-site Randomization and IP administration in the DESTINATION study is not possible by the end of the SOURCE Safety Follow-Up (Visit 20), a subject will not roll-over to the DESTINATION study.

Subjects aimed to roll over to the DESTINATION study will continue participation in the SOURCE study Safety Follow-Up (Visit 19 and Visit 20, 12 weeks) until the on-site DESTINATION randomization and IP administration can be conducted.

- If the subject is able to attend an on-site Visit 19 of the SOURCE study, they can be randomized into the DESTINATION study at this visit. During this visit the informed consent form, eligibility check, unscheduled safety labs, serum pregnancy test (if applicable) and randomization must be completed along with assessments as per Visit 2 in DESTINATION Table 1. If Visit 3 cannot be conducted on-site this can be conducted as a phone visit without IP administration. Please note the Home visit with IP administration alternative cannot be used until the first 2 IP doses are administered during an on-site visit.
- If the subject is able to attend an on-site Visit 20 of the SOURCE study, they can be randomized into the DESTINATION study at this visit. During this visit the informed consent form, eligibility check, unscheduled safety labs, serum pregnancy test (if applicable) and randomization must be completed along with assessments as per Visit 4 in DESTINATION Table 1. Visit 2 and Visit 3 will be skipped. If Visit 5 cannot be conducted on-site this can be conducted as a phone visit without IP administration. Please note the Home visit with IP administration alternative cannot be used until the first 2 IP doses are administered during an on-site visit.

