3.1.1 Data integration

Data from the predecessor studies will be integrated with the data from the LTE study. However, data will be reported separately for subjects initially enrolled in D5180C00007 from those initially in enrolled in D5180C00009, unless otherwise stated.

Subjects are assigned new enrolment codes (ecodes) in the LTE study from those assigned in the predecessor studies. The new ecodes will not overlap with those used in the predecessor studies. The SUTRA eCRF module in the database for the LTE study provides the decode link to allow subjects data across the studies to be integrated.

Ongoing AEs, concomitant medications and exacerbations will be recorded in both the predecessor study database and the LTE study database. If possible, they will be combined into one record for the purpose of analysis, based on the worst case (e.g., an ongoing AE recorded as mild in the predecessor study and recorded as moderate in the LTE study will be reported as one AE of moderate intensity).

Throughout this document reference to a particular week is in relation to Week 0 from the predecessor study (e.g., for study D5180C00007, Week 12 refers to 12 weeks after randomisation in the predecessor study; Week 64 refers to 12 weeks after enrolment into the LTE study).

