| Week 20 | 141 | 127-154 127-154 | | -154 | - | | | |
| Week 24 | 169 | 155-182 | | 155-182 | | 141-196 | | |
| Week 28 | 197 | 183-210 | | 183-210 | | - | | |
| Week 32 | 225 | 211-238 | | 211-238 | | - | | |
| Week 36 | 253 | 239-266 | | 239-266 | | - | | |
| Week 40 | 281 | 267-294 | | 267-294 | | - | | |
| Week 44 | 309 | 295-322 | | 295 | 295-322 | | - | |
| Week 48 | 337 | 323-350 | | 323-350 | | N/A | 309-364 | |
| Week 52 | 365 | 351-378 | | 351-378 | | 337-392 | N/A | |
| Follow-up Week 54 a | 379 | N/A | 351-399 | N/A | 351-399 | N | /A | |
| Week 56 | 393 | 379 | -406 | | | | - | |
| Follow-up Week 58 a | 407 | 386-427 | N/A | 386-427 | N/A | N | /A | |
| Follow-up Week 60 a | 421 | N/A | 400-441 | N/A | 400-441 | N | /A | |
| Week 60 | 421 | 407 | -434 | | - | | - | |

| Time Point Target | | Visit Window 1 | | Visit Window 2 | | Visit Window 3 | |
|------------------------|-----|-----------------|-----------------|-----------------|-----------------|-----------------|-----------------|
| Time Tomic | Day | D5180 C00007 | D5180 C00009 | D5180 C00007 | D5180 C00009 | D5180 C00007 | D5180 C00009 |
| Follow-up Week 64 a | 449 | 428-469 | N/A | 428-469 | N/A | N | /A |
| Week 64 | 449 | 435-462 | | 379-490 | | - | |
| Week 68 | 477 | 463-490 | | - | | - | |
| Week 72 | 505 | 491-518 | | - | | - | |
| Week 76 | 533 | 519-546 | | 491-574 | | 393-630 | 365-630 |
| Week 80 | 561 | 547-574 | | - | | - | |
| Week 84 | 589 | 575-602 | | - | | - | |
| Week 88 | 617 | 603-630 | | 575-672 | | | - |
| Week 92 | 645 | 631-658 | | - | | | |
| Week 96 | 673 | 659-686 | | - | | | |
| Week 100 | 701 | 687-714 | | - | | - | |
| EOT Week 104 | 729 | 715-749 | | 673-770 | | 631-812 | |
| Follow-up Week 110 | 771 | 750-791 | | - | | - | |
| Follow-up Week 116 | 813 | 792-833 | | 771-896 | | | - |

^a Only applicable for subjects who do not enrol into the LTE study.

| Time Point | Tanget Day | | Visit Window 2 | 2 |
|--------------------|------------|-----|----------------|------------|
| Time Point | Target Day | CCI | | Urinalysis |
| EOT Week 104 | 729 | | | 673-854 |
| Follow-up Week 110 | 771 | | | - |

In all cases above, no time points will be presented in summary tables or included in statistical analysis which do not correspond to the time points scheduled in the protocol for the variable in question. Listings of data will include all scheduled and unscheduled visits.

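### Appendix H 4 matches NAVIGATOR Visit 18 and SOURCE Visit 19 roll-overs to DESTINATION visits dated 2 weeks earlier, so the next scheduled dose is nominally 14 or 42 days away, and the short interval can fall within the overdose definition

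*Protocol*

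**What the plan says.** Appendix H 4 covers subjects who could not attend the predecessor end-of-treatment visit on site because of the pandemic. They stay in the predecessor safety follow-up, described as "NAVIGATOR study Safety Follow-Up (Visit 18 and Visit 19, 12 weeks") and "SOURCE study Safety Follow-Up (Visit 19 and Visit 20, 12 weeks"), until DESTINATION randomisation and dosing can take place on site.

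- **NAVIGATOR Visit 18.** The subject is randomised, with "unscheduled safety labs, serum pregnancy test (if applicable) and randomization must be completed along with assessments as per Visit 3 in" DESTINATION Table 1. For the following visit: "If Visit 4 cannot be conducted on-site this can be conducted as a phone visit without IP administration".
- **SOURCE Visit 19.** The same procedure applies, with assessments as for Visit 2. For the following visit: "If Visit 3 cannot be conducted on-site this can be conducted as a phone visit without IP administration".
- **Later routes.** NAVIGATOR Visit 19 is matched to DESTINATION Visit 5, and SOURCE Visit 20 to Visit 4. The visits in between are skipped.

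Appendix H also requires the first two DESTINATION doses to be given on site.

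Protocol Table 1 fixes each DESTINATION visit to a week with a ±5-day window, and Section 4.1 fixes the last dose at Week 100 and end of treatment at Week 104. The SAP (3.1.1) counts time the same way: "reference to a particular week is in relation to Week 0 from the predecessor study". SAP Table 3 dates the first NAVIGATOR follow-up visit: "Follow-up Week 58 a | 407 | 386-427".

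Protocol 8.4.3 states: "A dose in excess of 280 mg SC administered within a 2-week period is considered an overdose". SAP 2.2 lists an important-deviation code (10.22) for more than 700 mg in the same length of time.

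**The concern.** The earlier route in each study is tied to a DESTINATION visit whose date has already passed by 2 weeks. If the Table 1 calendar then continues unchanged, the second DESTINATION dose is scheduled 2 weeks after the first. If the second visit is held by telephone, the gap is 6 weeks or more. Neither is the nominal 4-week interval of the regimen under study.

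Two things are at stake. First, a site that follows Appendix H and Table 1 within their permitted windows can create an event that Section 8.4.3 requires it to report as an overdose within 24 hours, and Appendix H gives no warning of this. Sites are blinded, so they cannot tell which subjects are concerned. For placebo subjects re-randomised to tezepelumab, it would happen at first exposure. Second, this is a safety study of a Q4W regimen, and no planned summary isolates a shortened interval.

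**Working it through.** **Inputs.** DESTINATION Visits 2 to 7 at Weeks 52 (SOURCE only), 56, 60, 64, 68 and 72, each ±5 days (Protocol Table 1). Predecessor follow-up target days 407 and 449 for NAVIGATOR, 379 and 421 for SOURCE (SAP Table 3). Delivered dose 209 mg (Protocol Table 5, footnote). Thresholds 280 mg (Protocol 8.4.3) and 700 mg (SAP 2.2), each over 2 weeks.

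**Step 1: reproduce the SAP target days.** Day = 7 × week + 1, with follow-up at 6 and 12 weeks after end of treatment.

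- NAVIGATOR: 52 + 6 = 58, 7 × 58 + 1 = 407; 52 + 12 = 64, 7 × 64 + 1 = 449.
- SOURCE: 48 + 6 = 54, 7 × 54 + 1 = 379; 48 + 12 = 60, 7 × 60 + 1 = 421.

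All four agree with SAP Table 3, and the second visits agree with the 12-week follow-up in Appendix H.

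**Step 2: nominal gap to the next dose.** Gap = 7 × (next DESTINATION week − roll-over week).

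| Roll-over visit (week) | Matched visit (week) | Matched minus actual | Next visit: gap | If that visit is by telephone |
|---|---|---|---|---|
| NAVIGATOR 18 (58) | Visit 3 (56) | −14 days | Visit 4 (60): 14 days | Visit 5 (64): 42 days |
| SOURCE 19 (54) | Visit 2 (52) | −14 days | Visit 3 (56): 14 days | Visit 4 (60): 42 days |
| NAVIGATOR 19 (64) | Visit 5 (64) | 0 | Visit 6 (68): 28 days | Visit 7 (72): 56 days |
| SOURCE 20 (60) | Visit 4 (60) | 0 | Visit 5 (64): 28 days | Visit 6 (68): 56 days |

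Only the earlier route in each study is out of step.

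**Step 3: ranges.** With ±5 days on the DESTINATION visit, 14 days becomes 9 to 19 and 42 becomes 37 to 47. A second missed on-site visit gives 7 × (68 − 58) = 70 days. The documents do not give the window of the predecessor follow-up visit. Assuming ±5 days, the two ranges widen to 4–24 and 32–52; assuming ±7 days, to 2–26 and 30–54.

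**Step 4: cumulative dose for tezepelumab recipients.** 2 × 209 = 418 mg, which is above 280 mg and below 700 mg.

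- Gap of 13 days or less: both doses lie in one period of 14 calendar days, so the definition is met. With the roll-over visit on its target day, these are 5 (days 9 to 13) of the 11 permitted days (9 to 19).
- Gap of exactly 14 days: any 14 calendar days contain one dose (209 mg). The total is 418 mg only if both end days are counted. Counted that way, the Phase 2b arm given 280 mg every 2 weeks (Protocol 2.2) would total 2 × 280 = 560 mg, an overdose by design.
- Gap of 15 days or more: not met.

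**Step 5: cross-check against the SAP analysis windows.** In Visit Window 1, Day 407 lies in the Week 60 window (407–434), not Week 56 (379–406). Day 379 lies in the Week 56 window, not Week 52 (351–378). The SAP therefore classifies both roll-over visits differently from Appendix H.

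**The case against.** **The dating is an inference.** The SAP statement on counting weeks is a convention for that document, not an instruction to sites. The Table 3 follow-up rows carry a footnote limiting them to subjects who do not enrol in DESTINATION. Appendix H matches assessments and gives no date for the next dose, so a site could re-time it. This stands as a caution, but the scheduled week of a predecessor visit does not depend on whether the subject later enrols. No text provides for re-timing, and the later routes skip visits, which shows the calendar being kept.

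**A delayed roll-over is off Q4W anyway.** The last predecessor dose was at Week 48 (NAVIGATOR) or Week 44 (SOURCE), 10 weeks before roll-over. Section 6.2 tolerates a skipped dose and calls for contact with the study physician after two in a row. This stands for the 42-day branch, which is longer than planned but breaches no stated limit. It does not answer the short interval.

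**The SAP already reports a good deal.** It summarises delayed roll-overs and missed doses due to COVID-19 (8.5), lists every administration date (4.4) and undertakes to identify gaps from missed doses in the CSR (3.2.1). It would be wrong to say these subjects vanish into the Q4W data. However, those items concern missed doses and delays; a shortened interval would have to be worked out from the listing.

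**Stronger readings.** A reader might infer that the 2-week interval as such meets the overdose definition. The documents do not support this at the nominal 14 days, and it cannot apply to subjects given only placebo. A reader might also infer that a 4-week interval is impossible, or that 2 and 6 weeks are the only outcomes. The first depends on a predecessor window the documents do not give: under the assumed ±7 days, 28 days is not reached, but 26 and 30 are. The second overlooks the 10-week case in Step 3.

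**Conclusion.** The inconsistency holds for one route in each study. The matched visit is 14 days too early, and on the Table 1 calendar the next dosing visit is nominally 14 days after the roll-over dose (9–19), or 42 days (37–47) or more if the next visit is by telephone. For tezepelumab recipients the overdose definition can be met, and clearly is at 13 days or less. SAP code 10.22 would not pick this up.

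The conclusion rests on three assumptions: the predecessor follow-up visits fall at the weeks in SAP Table 3; sites keep to the Table 1 calendar after a delayed roll-over; and Section 8.4.3 refers to the cumulative amount over 2 weeks. The documents do not say how many subjects used these routes, so no effect on the adverse event rates or the exacerbation rate is claimed. This is a contradiction to reconcile, not evidence that overdoses occurred.

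**What to change.** **Protocol.** The sponsor should reconcile the NAVIGATOR Visit 18 and SOURCE Visit 19 bullets of Appendix H 4 with Table 1, the Q4W regimen and the Section 8.4.3 definition, including how the 2-week period is counted. The 280 mg in 8.4.3 and the 700 mg in SAP code 10.22 also need to be reconciled with each other. No interval, dose or threshold is proposed here.

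**SAP.** Flag subjects randomised through these two routes and report their first inter-dose interval, by treatment group, beside the delayed roll-over summary already planned in 8.5.

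**Cost.** A short protocol clarification or site letter, and one derived flag with one interval summary from dates already collected. If roll-over has closed, the SAP part can still be done and would show how many subjects were affected.
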